myeloma²¹. Although many cytokines can stimulate IL-6 production, in myeloma interleukin-1 β (IL-1 β) appears to be one of the major cytokines responsible for the paracrine production of IL-6 by marrow stromal cells²²⁻²⁵. The aberrant IL-1 β produced by the myeloma cells induces IL-6 production by bone marrow stromal cells which in turn supports the growth and survival of the myeloma cells²². The results of a recent clinical trial using IL-1 receptor antagonist (IL-1Ra) confirmed that IL-1Ra *in vivo* targeted the myeloma proliferative component. The median progression free survival (PFS) for the entire group of 47 patients was 37 months. The median PFS for patients without (n=22) and with (n=25) a decrease in their baseline hsCRP was 11 months and 103 months respectively (p<0.0001). The median overall survival (OS) for the 47 patients was 9.5 years. The median OS for patients without and with a decrease in their baseline hsCRP was 7.9 years and has not been reached, respectively (p=0.001). In SMM/IMM patients at high risk for progression to active myeloma, treatment with IL-1 inhibitors (IL-1Ra \pm Dex) results in an increased PFS and OS in patients that demonstrate a \geq 40% reduction in the baseline CRP compared to those who do not show this decrease. Toxicity included injection site reactions during the first month of therapy and asymptomatic neutropenia²⁶. The importance of IL-1 lies in the fact that small amounts of IL-1 β can induce large amounts of IL-6 in a paracrine fashion^{22,27}. Since IL-6 is a central myeloma growth factor, it appears that the myeloma proliferative component can be inhibited with IL-1Ra in early stage disease.

- 1.4 Patient and physicians desire a way to delay progression in patients with early stage MM. Patients with \geq 10% BMPCs and \geq 3 g/dL M-protein have a median time to progression to active MM of 2 years and patients with a high growth rate have an even shorter time to progression²⁸. Lenalidomide and dexamethasone (len/dex) are useful at targeting the non-proliferative myeloma compartment however patients with a high growth rate often relapse quickly on lenalidomide/dexamethasone. Since IL-1R inhibitors are effective at inhibiting the proliferative myeloma subset, early stage myeloma patients with an elevated growth rate (\geq 1%) may benefit from a combination of lenalidomide/dexamethasone and IL-1 receptor antagonist which is the focus of this trial.
- 1.5 There is a large body of literature describing the dosing of lenalidomide with dexamethasone and one publication describing the dosing of anakinra with dexamethasone²⁶ however the use of all three in a clinical trial has not been previously reported. Therefore, we will perform a Phase I Safety Run increasing doses of anakinra with lenalidomide and dexamethasone.
- 1.6 This study will be conducting in accordance with the Declaration of Helsinki and Good Clinical Practices Guidelines (GCP).

2.0 Goals

2.1 Primary Objective

2.11 Phase I: To determine the MTD/MAD of anakinra that can be combined with lenalidomide and dexamethasone.

2.12 Phase II: The primary goal of this trial is to compare the time to progression of the standard treatment arm (lenalidomide/dexamethasone) to the experimental arm (lenalidomide/dexamethasone + anakinra).

2.2 Secondary Objectives

2.21 To compare the response rate of the standard treatment arm (lenalidomide/dexamethasone) to the experimental arm (lenalidomide/dexamethasone + anakinra).

2.22 To compare the toxicity of the standard treatment arm (lenalidomide/dexamethasone) to the experimental arm (lenalidomide/dexamethasone + anakinra).

2.23 To compare the overall survival of the standard treatment arm (lenalidomide/dexamethasone) to the experimental arm (lenalidomide/dexamethasone + anakinra).

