The primary goal of this trial is to compare the time to progression of the standard treatment arm (Arm A) to the experimental arm (Arm B). We will conduct a randomized trial comparing the experimental arm against the standard treatment arm. We will enter 45 evaluable patients to each arm of the study using a 1:1 randomization scheme (Pocock et al, 1975). The stratification factors that will be used are listed in Section 5.0. The primary analysis will be a comparison of Arm A to Arm B using a one-sided log-rank test between the two Kaplan-Meier curves. This final analysis will take place after an approximate 24-month accrual period and after 52 total progressions have occurred or the last patient has been followed for at least 2 years (whichever occurs first). Additionally, we assume a constant accrual rate over the course of the study and that we will not have a significant lost to follow-up issue, as historically lost to follow-up rates in Mayo clinic trials have been $< 1\%$. A sample size of 45 evaluable patients per arm (90 total) provides 80% power to detect an improvement in median time to progression from 20 months to 40 months (a hazard ratio of 2.0), using a 1-sided log-rank test at a significance level of 0.05. A final decision regarding the level

of promise for the experimental regimen will take all factors into account including TTP, response rate, OS, adverse events, and other relevant factors. All patients meeting the eligibility criteria who have signed a consent form and have begun treatment will be evaluable for the primary endpoint.

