16.33 Secondary Outcome Analyses

The secondary endpoints listed below will be evaluated in each arm independently and will also be compared between the two arms in an exploratory manner.

16.331 Survival time is defined as the time from registration to death due to any cause. The distribution of survival time will be estimated using the method of Kaplan-Meier within each arm and compared between the arms using a one-sided log-rank test.

16.332 Overall response rate: The overall response rate will be estimated by the number of patients with an objective status of sCR, CR, VGPR, or PR divided by the total number of evaluable patients. All evaluable patients will be used for this analysis. Exact binomial 95% confidence intervals for the true overall response rate will be calculated within each arm and compared between the arms using Fisher's exact test.

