16.34 Adverse Events

All eligible patients that have initiated treatment will be considered evaluable for assessing adverse event rate(s). The maximum grade for each type of adverse event will be recorded for each patient, and frequency tables will be reviewed to determine patterns. Additionally, the relationship of the adverse event(s) to the study treatment will be taken into consideration.

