16.35 Over Accrual

If more than the target number of patients are accrued, the additional patients will not be used to evaluate the stopping rule or used in any decision making processes; however, they will be included in final point estimates and confidence intervals.

16.36 Data & Safety Monitoring:

16.361 The principal investigator(s) and the study statistician will review the study at least twice a year to identify accrual, adverse event, and any endpoint problems that might be developing. The Mayo Clinic Cancer Center (MCCC) Data Safety Monitoring Board (DSMB) is responsible

for reviewing accrual and safety data for this trial at least twice a year, based on reports provided by the MCCC Statistical Office.

- 16.362 Adverse Event Stopping Rules (These rules apply to Arm A and Arm B independently for patients in the randomized phase II portion of the study): The stopping rules specified below are based on the knowledge available at study development. We note that the Adverse Event Stopping Rule may be adjusted in the event of either (1) the study re-opening to accrual or (2) at any time during the conduct of the trial and in consideration of newly acquired information regarding the adverse event profile of the treatment(s) under investigation. The study team may choose to suspend accrual because of unexpected adverse event profiles that have not crossed the specified rule below.

Accrual will be temporarily suspended to both arms if at any time we observe events considered at least possibly related to study treatment (i.e. an adverse event with attribute specified as “possible”, “probable”, or “definite”) that satisfy either of the following:

- if 3 or more patients in the first 12 treated patients experience a grade 4 or higher non-hematologic adverse event at least possibly related to treatment.
- if after the first 12 patients have been treated, 25% of all patients experience a grade 4 or higher non-hematologic adverse event at least possibly related to treatment

We note that we will review Grade 4 and 5 adverse events deemed “unrelated” or “unlikely to be related”, to verify their attribution and to monitor the emergence of a previously unrecognized treatment-related adverse event.

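### Toxicity and survival are to be compared between arms, but the plan gives neither a between-arm estimate nor an interval, so it does not show how much harm the data can exclude

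*Combined protocol and SAP*

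**What the plan says.** Section 2.2 lists three secondary objectives, each worded as a between-arm comparison. Two concern endpoints where harm could appear: "To compare the toxicity of the standard treatment arm (lenalidomide/dexamethasone) to the experimental arm (lenalidomide/dexamethasone + anakinra" (2.22) and "To compare the overall survival of the standard treatment arm (lenalidomide/dexamethasone) to the experimental arm (lenalidomide/dexamethasone + anakinra" (2.23). Neither states a direction.

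The analyses given for them are:

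- **Survival (16.331).** Kaplan-Meier estimates within each arm, "compared between the arms using a one-sided log-rank test". The section states no direction, significance level, hazard ratio or confidence interval. Section 16.33 says the endpoints it lists will be "compared between the two arms in an exploratory manner".
- **Toxicity (16.34).** The maximum grade of each event type is recorded per patient, and "frequency tables will be reviewed to determine patterns". No between-arm difference, interval or test is named. The list of between-arm analyses in 16.33 holds only survival and response.
- **Response (16.332), for contrast.** Exact binomial 95% intervals in each arm, "compared between the arms using Fisher's exact test".

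Section 16.31 says that the final judgement of the regimen's promise "will take all factors into account including TTP, response rate, OS, adverse events" and other relevant factors.

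**The concern.** The decision whether to take anakinra forward is meant to weigh survival and adverse events against any gain in time to progression (TTP). That requires a statement, for each, of the estimated difference between arms and the range of differences compatible with the data. For survival the only between-arm statistic is a one-sided p-value. For toxicity there is none.

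The question is a live one for this combination. Section 1.5 says that use of all three drugs in a clinical trial has not been reported. Section 15.36 gives serious infections of 2% on anakinra against under 1% on placebo, in rheumatoid arthritis trials, and says that safety in immunosuppressed patients has not been evaluated. Neutropenia is a listed toxicity of both lenalidomide (15.17) and anakinra (15.37).

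**Working it through.** **1. The plan's own figure.** The only powered comparison is TTP (16.31): hazard ratio 2.0, one-sided 0.05, 80% power, 1:1 allocation. Events needed = 4(1.645 + 0.842)² / (ln 2)² = 51.5, so 52. Power at 52 events = Φ(ln 2 × √52 / 2 − 1.645) = Φ(2.499 − 1.645) = 0.80. This agrees with the plan. No event count or power is stated for survival or toxicity.

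**2. Expected deaths.** The documents give no survival rate, so I assume 3-year survival S of 90%, 80% or 70% in both arms, with exponential times. Other inputs are 90 patients, 24 months' uniform accrual and 24 months' further follow-up (16.31), so potential follow-up is uniform on 24-48 months. Section 18.13 requires no follow-up beyond 3 years after registration, so I cap it at 36 months. With λ = −ln(S)/36:

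deaths = 90 × {1 − [(e^(−24λ) − e^(−36λ))/λ + 12e^(−36λ)] / 24}

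For S = 80%: λ = 0.006198, and the bracket is (0.8618 − 0.8000)/0.006198 + 9.6 = 19.57. Deaths = 90 × (1 − 19.57/24) = 16.6.

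Across S = 90/80/70% the result is 8.3/16.6/25.1 deaths. Without the cap it would be 9.0/17.9/26.9.

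**3. What a survival analysis can show.** With d deaths the log hazard ratio has standard error about 2/√d. Power of a two-sided 5% test to flag a true hazard ratio of 2 against anakinra is Φ(ln 2 × √d / 2 − 1.96). The 95% interval is the estimate divided and multiplied by exp(1.96 × 2/√d).

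| Deaths | Power, two-sided 5% | Interval factor | Interval if observed HR is 1 |
|---|---|---|---|
| 8 | 16% | 4.0 | 0.25 to 4.0 |
| 17 | 30% | 2.6 | 0.39 to 2.6 |
| 25 | 41% | 2.2 | 0.46 to 2.2 |

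If the one-sided test is for benefit, then at 20 deaths and a true hazard ratio of 2 against anakinra it is significant with probability Φ(−1.645 − 1.550) = 0.0007. In every other trial it reads as not significant, as it usually would with no difference. The last column is what the plan omits: even equal observed survival would leave a hazard ratio of 2 inside the interval.

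**4. Toxicity, as an illustration.** Assume 4/45 against 10/45 patients with some Grade 3+ event. The difference is 22.2 − 8.9 = 13.3 points, with a Newcombe 95% interval of −2.0 to 28.4 (Fisher p = 0.14). A table by arm shows the counts. It does not show that the data are compatible with anything from a slight decrease to an excess of 28 points.

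**5. The plan's other reactions to harm.**

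- *Stopping rule (16.362).* "These rules apply to Arm A and Arm B independently". It counts only Grade 4+ non-hematologic events at least possibly related to treatment, and it suspends accrual. Applied after each patient up to 45 in an arm, it triggers with probability 0.022, 0.136, 0.607 and 0.935 at true rates of 5%, 10%, 20% and 30%. It therefore reacts to a high rate in one arm, whatever the rate in the other. A doubling from 5% to 10% would usually not trigger it.
- *Futility rule (16.32).* At 26 progressions the trial stops if the observed TTP hazard ratio, B over A, is at least 1. The probability is Φ(ln HR × √26 / 2): 0.50, 0.85 and 0.96 at true ratios of 1.0, 1.5 and 2.0. The stated conclusion is that an advantage has not been established, and the endpoint is neither survival nor toxicity.
- *Safety board review (16.361).* At least twice a year, with no comparative statistic named.
- *Fisher's test on response (16.332).* Sidedness is not stated, so it could show a lower response rate on anakinra.

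None of these estimates the between-arm difference in survival or toxicity.

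**The case against.** A reader might infer that no planned analysis can reveal harm from anakinra. The documents do not support that: the four elements in step 5 can all react to it, and Kaplan-Meier curves by arm would display a survival deficit. A reader might also take it as stated that the survival test is for benefit. Section 16.331 gives no direction; benefit is an inference from the one-sided primary test.

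Further points on the plan's side:

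- The primary objective (2.12) also says compare and is tested one-sided, so the verb alone does not require a two-sided test. This stands. The case rests on the missing estimates and on the role of survival and toxicity in the decision.
- The survival comparison is declared exploratory, and the final decision does not hang on its p-value. This stands and lowers the severity.
- A two-sided test would usually call a doubled death hazard not significant as well (step 3). This also stands, and it is why the interval matters more than the test.
- Descriptive adverse-event tables are a legitimate choice with 45 patients per arm, and risk differences can be worked out from counts by arm. That is true, but 16.34 does not say the tables are by arm or which events are of prime interest. Choosing events after seeing the tables weakens any comparison.
- Section 16.35 mentions final point estimates and confidence intervals. It does so only in dealing with over-accrual and names no endpoint.

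**Conclusion.** The concern holds as a reporting gap in objectives 2.22 and 2.23. The plan has safeguards that can react to harm, but its specified outputs do not quantify the survival or toxicity difference between arms, although both feed the final decision.

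The size rests on assumed 3-year survival of 70-90%, equal in both arms, exponential times and follow-up ending at 3 years. On that basis there would be about 8-25 deaths, 16-41% two-sided power against a hazard ratio of 2, and 95% intervals spanning a factor of about 2.2-4.0 either side of the estimate. The toxicity counts are illustrative only.

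The primary TTP design is unaffected. Given the exploratory status, the existing safeguards and the low power that any survival test would have, this is an improvement to consider.

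**What to change.** - **16.331:** report the survival hazard ratio (Arm B against Arm A) with its 95% confidence interval, and make the exploratory log-rank p-value two-sided.
- **16.34:** state that the tables are by arm. For a short list of events fixed in advance by the sponsor, report the risk difference between arms with a 95% confidence interval. Candidates are Grade 3+ infection, Grade 3+ neutropenia, and the related Grade 4+ non-hematologic events already used in 16.362.
- **Unchanged:** the one-sided primary TTP test and the sample size.

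The cost is a few sentences of plan text and a little more analysis. The exploratory survival p-value would look slightly less favourable if anakinra does better. No added patients or follow-up are needed.

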3.0 Patient Eligibility

Phase I only: Prior to discussing protocol entry with the patient, call the MCCC Registration Office (██████████) for dose level and to insure that a place on the protocol is open to the patient.

3.1 Inclusion Criteria

3.11 Age ≥ 18 years.

3.12 The following laboratory values obtained ≤ 7 days prior to registration.

- Absolute neutrophil count (ANC) $\geq 1700/\text{mm}^3$
- Platelet count $\geq 100,000/\text{mm}^3$
- Hemoglobin ≥ 8.0 g/dL
- SGOT (AST) ≤ 3 x upper limit of normal (ULN)
- Creatinine clearance ≥ 30 mL/min (as determined by Cockcroft-Gault equation*)

*Cockcroft-Gault Equations:

$$\text{Creatinine clearance for males} = \frac{(140 - \text{age})(\text{actual body weight in kg})}{(72)(\text{serum creatinine in mg/dL})}$$

$$\text{Creatinine clearance for females} = \frac{(140 - \text{age})(\text{actual body weight in kg})(0.85)}{(72)(\text{serum creatinine in mg/dL})}$$

Example: A woman aged 75, weight 50 kg and creatinine of 1.35 mg/dL has a calculated clearance of 28.

3.13 Diagnosis of multiple myeloma according to International Myeloma Working Group criteria and one of the following:

- SMM
- IMM
- newly diagnosed MM

Note: Patients with lytic disease and anemia are eligible

3.14 High risk disease defined by all of the following:

- $\geq 10\%$ bone marrow plasma cells
AND
- Abnormal serum free light chain (FLC) ratio (< 0.26 or > 1.65) by serum FLC assay
AND
- Monotypic Plasma Cell S-phase $\geq 0.3\%$

3.15 Measureable level of M-protein > 1 g/dL on serum protein electrophoresis or > 200 mg of M-protein on a 24 hour urine protein electrophoresis.

3.16 Negative tuberculosis (TB) testing (Quantiferon – TB blood test or skin test) ≤ 7 days prior to registration.

3.17 ECOG performance status (PS) 0, 1 or 2 ([Appendix I](#)).

- 3.18 Provide signed informed consent.
- 3.19a Negative (serum or urine) pregnancy test done ≤ 7 days prior to registration, for women of childbearing potential only.
NOTE: A second pregnancy test must be performed within 24 hours prior to the start of lenalidomide. The subject may not receive lenalidomide until the study doctor has verified that the results of these pregnancy tests are negative.
- 3.19b Willing to return to enrolling institution for follow-up (during the Active Monitoring Phase of the study).
- 3.19c Willing and able to comply with the requirements of the Revlimid REMS™ program.
- 3.19d Females of childbearing potential must be willing to adhere to the scheduled pregnancy testing as required by the Revlimid REMS™ program.
- 3.2 Exclusion Criteria
- 3.21 Prior treatment with any other agent that may affect M-protein ≤ 30 days prior to registration.
- 3.22 Acute/chronic infections, open wounds, or any active infection requiring intravenous antibiotic therapy ≤ 12 weeks prior to registration.
- 3.23 Other active malignancy (≤ 3 years) prior to registration.
Exceptions: Basal cell skin cancer or carcinoma-in-situ of the cervix or low-risk prostate cancer after curative therapy
- 3.24 Any of the following because this study involves an investigational agent whose genotoxic, mutagenic and teratogenic effects on the developing fetus and newborn are unknown:
- Pregnant women
 - Nursing women
 - Men or women of childbearing potential who are unwilling to employ adequate contraception
- 3.25 NYHA Class 3 or 4 CHF symptoms
- 3.26 Other concurrent chemotherapy, radiotherapy, or any ancillary therapy considered investigational.
- NOTE:** Bisphosphonates are considered to be supportive care rather than therapy, and are thus allowed while on protocol treatment.

4.0 Test Schedule

Tests and Procedures	Active Monitoring				
	≤7 Days Prior to Registration	End of Cycles 1-3 then end of every third cycle and end of treatment ⁷	Pre-treatment every cycle ⁵	Mid-cycle every cycle ¹⁰	End of Cycle 6 and Cycle 12, then yearly
Complete medical history	X				
Adverse Event monitoring	X	X ⁹	X		
Physical exam, including weight and vital signs	X	X			
Height	X				
Performance status (ECOG scale)	X	X			
EKG	X				
Hematology group (WBC, ANC, Hgb, PLT)	X	X ¹⁰	X ⁵	X	
Chemistry group (glucose, alkaline phosphatase; total bilirubin; SGOT (AST); serum creatinine, creatinine clearance, calcium, LDH and TSH ⁶)	X	X			
Beta ₂ -microglobulin, high sensitivity C-reactive protein	X	X			
SPEP and UPEP (24 hours collection)	X	X			
Circulating plasma cells (PBLI/PCLI)	X	X			
Immunofixation serum and urine	X ²	X ⁴			
Immunoglobulin free light chain (MML)	X	X			
Involved Immunoglobulin (IgA, IgG, IgM)	X	X ³			
X-ray skeletal survey (incl long bones) or low dose full body CT	X ²				X
Bone marrow aspirate and biopsy, myeloma FISH, metaphase cytogenetics, Plasma cell proliferation assay and flow cytometry	X ²	X ⁴			X
Serum or urine pregnancy test	X ¹	X ¹	X ^{1,5}		
Tuberculosis testing (Quantiferon blood test or skin testing)	X				
Register patient into Revlimid REMS® program	X				
Prescribe lenalidomide via Revlimid REMS		X ^{5,8}	X		
Research per IRB 521-93, optional ^R	X ^R				X ^R

- 1) Pregnancy tests for females of childbearing potential. A female of childbearing potential (FCBP) is a sexually mature female who: 1) has not undergone a hysterectomy or bilateral oophorectomy; or 2) has not been naturally postmenopausal for at least 24 consecutive months (i.e., has had menses at any time in the preceding 24 consecutive months). Pregnancy tests must occur ≤7 days prior to registration and again within 24 hours prior to initiation of lenalidomide. FCBP with regular or no menstruation must have a pregnancy test weekly for the first 4 weeks and then every 28 days while on therapy (including breaks in therapy); at discontinuation of lenalidomide and at Day 28 post the last dose of lenalidomide. Females with irregular menstruation must have a

pregnancy test weekly for the first 4 weeks and then every 14 days while on therapy (including breaks in therapy), at discontinuation of lenalidomide and at Day 14 and Day 28 post the last dose of lenalidomide (see [Appendix VI](#): Risks of Fetal Exposure, Pregnancy Testing Guidelines and Acceptable Birth Control Methods).

- 2) ≤ 30 days prior to registration
 - 3) Specific testing required only if used to assess disease response
 - 4) Required to document complete response; if response, repeat (mail-in acceptable) to confirm response at ≥ 4 weeks. Bone marrow biopsy does not need confirmation. (Bone marrow biopsy will occur one time as clinically indicated.)
 - 5) Only enough lenalidomide for one cycle of therapy will be supplied to the patient each cycle. After the first 3 months, the drug may be mailed out to the patient if clinical evaluation and blood tests can be obtained per test schedule and mailed/faxed to Mayo Clinic, and patient can return at least every 3 months for follow up to Mayo Clinic. In place of physical exam, RNs will phone patient for adverse event assessment. All unused study drug must be returned to Mayo Clinic and all study drug must be accounted for. CBC and pregnancy testing may be done at local clinic.
 - 6) TSH to be repeated every three months, for patients on active treatment.
 - 7) ± 7 days
 - 8) Lenalidomide must be prescribed through and in compliance with Celgene's Revlimid REMS program. Prescriptions must be filled within 7 days.
 - 9) The patient should be contacted by a nurse 30 days (± 2 days) after the last dose of study treatment (or at the time of initiation of subsequent treatment if started before 30 days) to check if the patient has experienced any late adverse events. Grade 3 or higher adverse events and all serious adverse events (SAEs) at least possibly related to study treatment and deaths due to any cause should be reported as a late adverse event on the event monitoring form if they were not already reported on the nadir/AE form for the last cycle and they occurred prior to any subsequent treatment.
 - 10) CBC should be done weekly during Cycle 1. After Cycle 1, CBC should be done pre-treatment and mid-cycle every cycle. CBC should also be done at the end of treatment. CBC testing may be done at local clinic.
- R Research funded (see [Section 19.0](#)). Will be charged to study and not to patient's account.

5.0 Grouping/Stratification Factors:

